4. AMENDMENTS AND UPDATES

None.

5. MILESTONES

Milestone	Planned Date
IRB/IEC approval	APR 2022
Start of data collection	APR 2022
End of data collection	APR2024
Study progress report 1	Not applicable
Topline analysis	After visit 2 of the LPI
Reg. in the EU PAS register	Not applicable
Final report of study results:	JUL 2024

6. RATIONALE AND BACKGROUND

6.1 MEDICAL BACKGROUND

According to the Global Initiative for Chronic Obstructive Lung Disease (GOLD), Chronic Obstructive Pulmonary Disease (COPD) is a common, preventable, and treatable disease with an estimated global prevalence of almost 300 million in 2017 [I, II]. By 2030, it is predicted that COPD will be the fourth-leading cause of death worldwide [III]. COPD is particularly prevalent in smokers and ex-smokers, people aged ≥ 40 years, and men [IV]. Disease characteristics comprise persistent respiratory symptoms and airflow limitation, usually resulting from significant exposure to noxious particles or gases, like tobacco smoke, air pollution or other environmental exposures [II]. The inhalation of such noxious substances triggers an abnormal inflammatory response in the lung leading to increased mucus production, tissue remodeling, and connected with this, to a narrowing of the air passages in the lower respiratory tract. As a result, the pulmonary parenchyma is destroyed, and pulmonary emphysema is caused. Over time, there are further systemic consequences, such as myopathy, osteoporosis, cor pulmonale, and hypertension with severe restriction of physical functioning. Recurrent acute exacerbations (e.g., due to pulmonary infections) bring about a further deterioration in the condition of the lungs [V]. In COPD patients, physical activity is reduced early in disease progression, as of GOLD Stage 2 [VI]. More recent evidence from large placebo controlled clinical trials indicates that COPD patients are experiencing a steeper absolute decline in lung function with GOLD 2 airflow limitation than with GOLD 3 and 4 [VII]. Those observations suggest the importance of early optimal treatment of the disease.

The main goal in COPD treatment is achievement of disease control and consequently, an improvement of health-related quality of life (HRQoL). Giving to the GOLD 2021 strategy

report, long-acting bronchodilators such as long-acting muscarinic antagonists and long-acting β_2 -agonists are the basis of maintenance therapy for patients with moderate-to-very severe COPD [II].

Beside the pharmacological compound, matching each patient with the most appropriate inhaler is important for an optimal inhaler technique and drug delivery [VIII-XIII]. These days, numerous inhaler devices for maintenance treatment in COPD patients are available on the market, but each class of device has a different approach to inhalation and therefore, requires distinct handling techniques. However, the correct usage of the respective inhaler is a prerequisite for achievement of maximal clinical benefit. Unfortunately, inhalers are often not considered as an important part of the treatment [X]. Discordance especially with prescribed dry powder inhalers (DPIs) was seen in 40% of COPD patients, suggesting that many COPD patients do not generate adequate inspiratory force to overcome prescribed DPIs resistance during normal use [XIII]. Therefore, when using a DPI, COPD patients with suboptimal peak inspiratory flow rate (PIFR) may not achieve the greatest possible drug deposition and efficacy [XIII]. Consequently, maximal clinic benefit might be unattainable for those patients.

The Respimat[®], an active soft-mist inhalation device, allows COPD patients to inhale without effort and can be used irrespective of the PIFR a patient can generate [XIV, XV]. It is well accepted by patients due to its easy inhalation and handling characteristics which is an important factor for treatment compliance [XVI, XVII, XVIII]. Additionally, Soft MistTM Inhaler (SMIs) have a lower intrinsic resistance and do not require a high inspiratory flow rate for optimal drug delivery in comparison to DPIs [XIX].

6.2 DRUG PROFILE

Tiotropium bromide is the first once-daily, long-acting anticholinergic bronchodilator for the maintenance therapy of patients with COPD and is available in two formulations in many countries: an aqueous solution (5 μ g) delivered via the Respimat[®] SMI [XX] and a dry powder (18 μ g) delivered via the breath-actuated Spiriva[®] HandiHaler[®] device (DPI, both formulations: Boehringer Ingelheim Pharma GmbH & Co KG, Ingelheim am Rhein, Germany) [XXI].

Numerous controlled trials, including either or both formulations, have shown that tiotropium provides at least a 24-hour sustained improvement in airflow, reduced hyperinflation, and shortness of breath, as well as a reduced risk of exacerbations and associated hospitalizations, resulting in an increased HRQoL [XXII-XXVIII].

6.3 ASSESSMENT OF QUALITY OF LIFE

Various questionnaires on HRQoL are used to try assessing COPD patients' health status and physical state. The Clinical COPD questionnaire (CCQ) has been developed and validated in the Netherlands especially for COPD patients by Jan Kocks et al. in 2006 [XXIX] to categorize

patients' impairments generally and focus patients' treatment on their specific needs. The CCQ is easy to administer, and it takes less than a few minutes to complete. CCQ is used to monitor the clinical control of COPD covering the last 7 days prior to request. It consists of 10 questions, covering 3 domains: symptom domain (4 items [#'s 1,2,5,6]); functional status domain (4 items [#'s 7,8,9,10]) and mental status domain (2 items [#'s 3,4]). The questionnaire is responsive to intervention and has been translated and validated in over 140 languages [XXX]. In a head-to-head comparison of COPD Assessment Test (CAT) and CCQ the patients preferred the latter as it reflected their status better than CAT by giving more details on breathing problems which was more important for them than sleep or energy [XXX]. CCQ has been given maximum ranking in "COPD wellness tools" overview by the International Primary Care Respiratory Group (IPCRG) [XXXI]. The clinical CCQ is a well-established tool to evaluate COPD patients self-reported outcomes [XXIX, XXXII, XXXIII]. A difference from -0.2 points corresponds to 50% of the minimal clinically important difference for a CCQ of -0.4 points [XXIX, XXXII]. Patients with a worse CCQ (score of ≥ 2) are expected to have a CCQ score that is on average 0.2 points higher (i.e., worse health status) than patients with an acceptable CCQ score for moderate disease (score of < 2) [XXXIV]. Thus, a change of -0.2 points will be used in this NIS to explore whether there is an improvement in CCQ after switching the device without changing the pharmacological compound although the setting in this NIS is different from the validation studies.

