7. RESEARCH QUESTION AND OBJECTIVES

The objective of this non-interventional, observational study is to assess whether changing COPD patients from a dry powder inhaler (HandiHaler®) to a soft mist inhaler (Respimat®), without changing the pharmacological compound, will lead to an improvement in CCQ score* and in the scores of the three subdomains: symptoms (4 items), functional state (4 items) and mental state (2 items) during a study period of approximately 8 weeks. Each of the 10 CCQ questions is scored by the patient on a 7-point scale between 0 and 6 at baseline and at the end of the observation after approximately 8 weeks. The sum of the scores divided by 10 gives the CCQ score, which measures the health and functional status.

The functional state score is a calculation of the sum of the 4 items (#'s 7, 8, 9, 10) divided by 4, the symptom score is calculation of the sum of the 4 items (#'s 1, 2, 5, 6) divided by 4 and the mental state score is a calculation of the sum of the 2 items (#'s 3, 4) divided by 2. More details, e.g., how to handle missing data, will be described in the statistical analysis plan.

CCQ values can be interpreted as: acceptable (CCQ < 1); acceptable for moderate disease (1 ≤ CCQ < 2); instable-severe limited (2 ≤ CCQ < 3); very instable-very severe limited (CCQ ≥ 3) [XVI,XVII]. As a CCQ ≥ 2 is as well associated with an increased mortality [XXVIII], this value will be used as the cut-off for the current non-interventional study.

Our hypothesis is that patients with a worse CCQ (= high CCQ of ≥ 2) at baseline will benefit the most when changing from the DPI Spiriva® HandiHaler® to the SMI Spiriva® Respimat®.

Note: Patients will be included into the study independently of their CCQ at baseline.

*CCQ score means CCQ overall score, unless otherwise stated

Primary objective:

The primary objective of the NIS is to assess proportion of patients achieving a 0.2 points decrease in the CCQ score between baseline and after approximately 8 weeks of treatment) in patients with high CCQ baseline score (≥ 2).

Secondary objectives:

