8.3.2 Outcomes

8.3.2.1 Primary outcomes

- Outcome type: primary
- Outcome name: "**Improvement**" defined as 0.2 points decrease in the CCQ score between baseline and visit 2 in patients with high CCQ baseline score (≥ 2)

- Time frame: between baseline (= visit 1) to approximately 8 weeks after switching from Spiriva® HandiHaler® to Spiriva® Respimat® (= visit 2)
- Safety Issue: No

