8.5 STUDY SIZE

It is expected that half of the patients included will have CCQ score of ≥ 2 (high CCQ).

Primary endpoint: Assuming 40% of high CCQ score patients have a 0.2 improvement in CCQ score from baseline at 8 weeks on treatment, then with a sample size of 100, the 95% CI for the response rate will be: (0.304, 0.496).

Secondary endpoint: Assuming 30% of all patients have a 0.2 improvement in CCQ score from baseline at 8 weeks on treatment, then with a total sample size of 200, the 95% CI for the response rate will be (0.236, 0.364).

With a dropout rate of 10%, a total of about 225 patients will be needed.

Sample size assumes that Respimat® is better compared to HandiHaler® and patients will improve their CCQ scores once switched to Respimat®. The sample size calculation/justification can only provide a rough estimate of the statistical power in such an exploratory real-world setting. Recruitment will continue until the minimum sample size is achieved.

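### Both responder outcomes use half the plan's own MCID, with no visible result at 0.4 or for worsening, and one of the two reasons given for 0.2 is not credible

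*Combined protocol and SAP*

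**What the plan says.** Section 6.3 gives two reasons for the threshold. The first is its relation to the MCID: "A difference from -0.2 points corresponds to 50% of the minimal clinically important difference for a CCQ of -0.4 points". The second is a comparison of patient groups: "Patients with a worse CCQ (score of ≥ 2) are expected to have a CCQ score that is on average 0.2 points higher" than those scoring below 2. It then concludes: "Thus, a change of -0.2 points will be used in this NIS to explore whether there is an improvement in CCQ", and concedes that the setting differs from the validation studies.

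Section 8.3.2.1 labels the primary outcome as improvement, "defined as 0.2 points decrease in the CCQ score between baseline and visit 2", in patients with baseline CCQ of at least 2. Section 8.3.2.2 uses the same cut-off for all patients. Section 8.7.1 makes it a decrease of at least 0.2, reported as one proportion with a 95% CI. Mean changes in CCQ are secondary outcomes in both populations.

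Section 7 describes four CCQ bands: below 1, 1 to below 2, 2 to below 3, and 3 or more. Section 8.5 expects half of the patients at 2 or above and sizes the study by "Assuming 40% of high CCQ score patients have a 0.2 improvement in CCQ score from baseline at 8 weeks on treatment", with 30% for all patients. Section 8.1 specifies a single arm with patients as their own controls. Section 8.7 rules out formal testing. The limitations in section 8.9 discuss selection and information bias but not regression to the mean.

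**The concern.** There are two separate issues.

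The first is the meaning of the responder rate. A complete CCQ is ten items scored 0 to 6 and divided by 10, so a 0.2 decrease is two one-step item changes. The outcome is called improvement, and section 6.5 treats week 8 as the point at which therapeutic success is judged. Yet no visible responder result is given at the value the protocol calls clinically important, and none shows how many patients got worse. Part of the stated support for 0.2 is a group difference that does not fit the plan's own description of the scale.

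The second is interpretation. With no comparator and no reference rate, the reader has nothing against which to judge the observed proportion. The primary population is chosen because its baseline score is high, so some of it will fall at visit 2 through regression to the mean alone. In a descriptive study the reported proportion is the message, and it could be read as a device benefit.

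**Working it through.** **The plan's own figures.** Wald interval, p ± 1.96·√(p(1−p)/n):
- 40%, n = 100: 0.40 ± 1.96·√(0.24/100) = 0.40 ± 0.096, giving 0.304 to 0.496.
- 30%, n = 200: 0.30 ± 1.96·√(0.21/200) = 0.30 ± 0.0635, giving about 0.236 to 0.364.
- 10% dropout: 200/0.9 = 222.2, so 223, against a stated figure of about 225.

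All three reproduce. The sample-size arithmetic is not at fault.

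**Threshold against MCID.** 0.2/0.4 = 50%, as section 6.3 says.

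**The between-group gap.** Take the cut at 2 with half the patients on each side (section 8.5) and assume a roughly normal score. The difference between the two group means is then 2·√(2/π)·SD = 1.596·SD.
- For a gap of 0.2: SD = 0.2/1.596 = 0.125, about 0.13 on a 0 to 6 scale.
- The documents give no baseline SD. Assumed SDs of 0.8, 1.0 and 1.2 give gaps of 1.28, 1.60 and 1.91. Truncating the distribution to 0 to 6 gives 1.25, 1.52 and 1.75.
- A check without normality: suppose only 10% of the high group score 3 or more, the rest of it sit exactly at 2.0, and every low-group patient is at 1.9. The high-group mean is then at least 0.1·3 + 0.9·2 = 2.1, so the gap is already at least 0.2. Any realistic spread over the four bands in section 7 makes it larger.

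**Responders with no true change.** The documents give no SD of change and no test-retest figure, so these inputs are assumptions: a stable true score with mean 2 and between-patient SD 0.8 to 1.0; independent error at each visit with within-patient SD 0.2 to 0.5; scores rounded to 0.1 and kept within 0 to 6; high-CCQ group defined by observed baseline of at least 2. Simulated results:

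| Within-patient SD | High CCQ, drop ≥ 0.2 | High CCQ, drop ≥ 0.4 | All patients, drop ≥ 0.2 |
|---|---|---|---|
| 0.2 | 34% | 13% | 29–30% |
| 0.3 | 42–43% | 25–26% | 36% |
| 0.4 | 47–49% | 34–35% | 39% |
| 0.5 | 51–53% | 40–41% | 41% |

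**Separating the two mechanisms.** Without selection on baseline, the SD of change is √2 times the within-patient SD: 0.28, 0.42, 0.57 and 0.71. On the 0.1 grid, P(drop ≥ 0.2) = Φ(−0.15/SD of change), about 30%, 36%, 40% and 42%. This agrees with the all-patient column. The excess in the high-CCQ column is regression to the mean.

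**The case against.** The half-MCID choice is disclosed, it stands as a reason independent of the group comparison, and the protocol says it is using 0.2 to explore. Nothing is decided on it: there is no test, and 40% and 30% only set the expected CI width. All of that stands.

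The group-gap sentence cites a source that is not available here, so it may be a poor paraphrase rather than a wrong number. A reader might infer that the gap is arithmetically impossible. It is not: on the 0.1 grid, scores clustered at 1.9 and 2.0 would give a gap as small as 0.1. The supportable statement is that it is implausible and inconsistent with the bands in section 7.

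A reader might also infer that random variation alone explains the planned 40%, or that this follows from the faulty sentence. Neither is supported. The no-change rate comes from the small threshold, the single arm and the selection on baseline, and its size depends on variability that the documents do not report. At a within-patient SD of 0.2 the high-CCQ figure is 34%, below 40%. Without the selection, 40% is reached only in the upper part of the assumed range.

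Mean and median changes will be reported and can be compared with 0.4, but they do not give a responder proportion. Finally, parts of the analysis text are redacted and further detail is deferred to a later SAP. A 0.4 analysis is therefore absent only from the visible outcomes; its absence from the whole plan cannot be shown.

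**Conclusion.** The concern holds in a limited form, as a cheap improvement rather than an error in the primary analysis. The 0.2 cut-off is half the plan's MCID, and the visible responder outcomes use nothing else. The between-group reason should not support it: the gap needs an SD of about 0.13, where assumed SDs of 0.8 to 1.2 give about 1.3 to 1.9 points, and it would be the wrong kind of evidence for a within-patient threshold even if correct.

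Under the stated assumptions and no device effect, about 34 to 53% of high-CCQ patients and 29 to 41% of all patients would count as improved at 0.2. In the high-CCQ group 13 to 41% would do so at 0.4. Rates near the planned 40% and 30% would therefore not by themselves point to the device. It would be wrong to conclude that moving to 0.4 cures this. It lowers the no-change rate but leaves a single arm without a reference rate.

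**What to change.** - Keep the 0.2 decrease as the primary threshold.
- In 8.3.2.2 and 8.7.1, add the proportion with a decrease of at least 0.4, with 95% CI, in the high-CCQ and all-patient populations.
- Beside each, report the proportions worsening by at least 0.2 and at least 0.4. Note that only the all-patient comparison of improving with worsening is free of the selection on baseline CCQ; in the high-CCQ group, improvement exceeds worsening even with no true change.
- State that any claim of clinically important improvement rests on the 0.4 result, and that neither rate alone shows a device effect.
- Name regression to the mean in 8.9.
- Remove or correct the 0.2 between-group sentence in 6.3.

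Section 8.7 has the SAP issued before database lock, so this can still be pre-specified there. The data are already collected. The cost is a few table rows and some sentences; the downside is that the 0.4 rate will be lower than the 0.2 rate.

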6.4 SITUATION IN SWITZERLAND

In Switzerland, both devices, the Spiriva® Respimat® SMI as well as the Spiriva® HandiHaler® DPI, are approved treatment options for COPD patients. Beside similar exacerbation and bronchodilator efficacy [XXIV, XXVIII], their safety and pharmacokinetic profiles are similar to each other [XXXV, XXXVI, XXXVII]. However, in Switzerland, life expectancy is one of the highest in Europe [XXXVIII] and therefore, it can be considered that mean age in Swiss COPD patients might be higher than in the other European countries. Thus, Swiss COPD patients might be faced with difficulties in preparation and handling of the device. The Respimat® device was developed to fulfil patients' and physicians' needs for an easy usability and might be an appropriate device in older patients who suffer from comorbidities correlated to impaired mobility such as Parkinson's disease, arthritis/arthrosis, and rheumatism [XXXIX]. In those patients, it seems to be important to follow up the ability for correct usage of their device to ensure adequate COPD maintenance therapy. Since there are no other Tiotropium devices (generic drugs) available on the Swiss market, COPD patients from Switzerland represent an ideal cohort to assess whether there is an improvement in clinical control of COPD when switching the patients from the DPI to the respective SMI without changing the active agent.

6.5 RATIONALE

The current non-interventional study (NIS) aims to evaluate whether in a real-world COPD patient setting and by not altering the pharmacological compound the change from the Spiriva® HandiHaler® to the Respimat® will lead to improvements in HRQoL including physical function, and dyspnea.

Based on the previous mentioned background, this NIS has been designed to assess whether changing COPD patients from a dry powder inhaler (HandiHaler®) to a soft mist inhaler (Respimat®), without changing the pharmacological compound, will lead to an improvement in HRQoL. Therapeutic success will be assessed at week 8 which is the mean time between two medical appointments in COPD patients. The well-established and commonly used CCQ will be used to assess changes in HRQoL in switching patients. [REDACTED]

will be collected to characterize the population of COPD patients which is intended for a switch to the SMI device.

7. RESEARCH QUESTION AND OBJECTIVES

The objective of this non-interventional, observational study is to assess whether changing COPD patients from a dry powder inhaler (HandiHaler®) to a soft mist inhaler (Respimat®), without changing the pharmacological compound, will lead to an improvement in CCQ score* and in the scores of the three subdomains: symptoms (4 items), functional state (4 items) and mental state (2 items) during a study period of approximately 8 weeks. Each of the 10 CCQ questions is scored by the patient on a 7-point scale between 0 and 6 at baseline and at the end of the observation after approximately 8 weeks. The sum of the scores divided by 10 gives the CCQ score, which measures the health and functional status.

The functional state score is a calculation of the sum of the 4 items (#'s 7, 8, 9, 10) divided by 4, the symptom score is calculation of the sum of the 4 items (#'s 1, 2, 5, 6) divided by 4 and the mental state score is a calculation of the sum of the 2 items (#'s 3, 4) divided by 2. More details, e.g., how to handle missing data, will be described in the statistical analysis plan.

CCQ values can be interpreted as: acceptable (CCQ < 1); acceptable for moderate disease (1 ≤ CCQ < 2); instable-severe limited (2 ≤ CCQ < 3); very instable-very severe limited (CCQ ≥ 3) [XVI,XVII]. As a CCQ ≥ 2 is as well associated with an increased mortality [XXVIII], this value will be used as the cut-off for the current non-interventional study.

Our hypothesis is that patients with a worse CCQ (= high CCQ of ≥ 2) at baseline will benefit the most when changing from the DPI Spiriva® HandiHaler® to the SMI Spiriva® Respimat®.

Note: Patients will be included into the study independently of their CCQ at baseline.

*CCQ score means CCQ overall score, unless otherwise stated

Primary objective:

The primary objective of the NIS is to assess proportion of patients achieving a 0.2 points decrease in the CCQ score between baseline and after approximately 8 weeks of treatment) in patients with high CCQ baseline score (≥ 2).

Secondary objectives:

Secondary objectives of the NIS are the assessment of the proportion of patients achieving a 0.2 points decrease in the CCQ score between baseline and after approximately 8 weeks of treatment independently from CCQ baseline score, the mean change in CCQ score and in the three CCQ domains symptom, mental state, and functional state domain in all patients and in patients with high CCQ baseline score (≥ 2) between baseline and visit 2 (approximately at week 8 after visit 1), breathlessness based on mMRC score at baseline, visit 2 (approximately at week 8 after visit 1), and change in mMRC score between baseline and visit 2 (approximately at week 8 after visit 1),

Safety data of COPD patients switching from Spiriva® HandiHaler® to Spiriva® Respimat® will be collected descriptively and are not a separate objective of the NIS.

